## Figure:

- Percent change from baseline in target lesions over time (spider plot)
- Best Change from baseline in target lesions (waterfall plot)

- K-M plot of DOR for responders based on investigator assessment only when number of responder is not few
- K-M plot of DOR for responders based on central review assessment only when number of responder is not few
- K-M plot of PFS for safety population. Two sets of figures, one based on investigator assessment and the other based on central review assessment, will be provided.
- Subgroup K-M plot of PFS analysis by prior line of therapies (<=1 and >=2) for subjects with pancreatic cancer safety population based on central review assessment
- K-M plot of OS for safety population
- Subgroup K-M plot of OS analysis by prior line of therapies (<=1 and >=2) for subjects with pancreatic cancer safety population

## Listing:

The following will be listed for all subjects:

- Tumor lesion measurements
- Tumor evaluation at each visit
- Subject level efficacy for all treated subjects tumor best overall response (BOR), maximum response in tumor burden, PFS, death indicator
- Duration of response for responders BOR, time to response, time on therapy, response duration, response duration after treatment discontinuation, reason for treatment discontinuation
- Survival survival status, first dose date, last dose date, first subsequent anti-cancer therapy date, last known alive date, death date, time to death

For the above listings except for survival, assessment performed by investigator and central review committee will be listed separately.

## 7.6 Safety

Unless otherwise specified, all analyses will be performed using the safety population.

Adverse events (AEs) will be coded according to the most current version of MedDRA and be graded using the NCI Common Terminology Criteria for Adverse Events (CTCAE) version *4.03*. Treatment-related AEs are those events with relationship to study treatment "Related" as recorded on the CRF. If the relationship to study treatment is missing, the AE will be considered as treatment related.

Listing of adverse events will include all enrolled subjects, as SAEs and deaths are collected pretreatment. Summaries of adverse events will be for treatment-emergent AE (TEAE) that is defined as adverse event starts or severity becomes worse after the first dose and within 100 days of last study therapy. AEs and treatment-related AEs will be tabulated by descending frequency of SOC and descending frequency of PT within each SOC, unless specified otherwise.

When reporting adverse events by CTC grade, summary tables will be provided based on the event with worst CTC grade (independent of relationship to study medication). Subjects will only be counted (1) once at the preferred term (PT) level, (2) once at the system organ class (SOC) level, and (3) once in the 'Total subject' row at their worst CTC grade, regardless of SOC or PT.

The analysis of laboratory results will be based on safety population with data. Laboratory results will be categorized according to NCI CTCAE (version *4.03*) grade. Baseline is defined as the last non-missing measurement prior to the first dosing date and time.

## 7.6.1 Deaths

All deaths during the study will be summarized for cause of deaths. All recorded deaths for enrolled population will be listed.

### Summary:

- All deaths, reasons for death
- Deaths within 30 days of last dose received, reasons for death
- Deaths within 100 days of last dose received, reasons for death

## 7.6.2 Serious Adverse Events

Overall summary of SAEs and treatment-related SAEs by worst CTC grade will be presented by SOC/PT. By-subject SAE listing will be provided for the enrolled population.

### Summary:

- Summary of SAEs by worst CTC grade (Grade 1, 2, 3, 4, 3-4, 5) presented by SOC/PT
- Summary of treatment-related SAEs by worst CTC grade (Grade 1, 2, 3, 4, 3-4, 5) presented by SOC/PT

Summary of treatment-related SAEs include SAEs that are cabiralizumab-related or nivolumab-related.

By-subject listing of SAEs will be provided

#### 7.6.3 Adverse Events Leading to Discontinuation of Study Therapy

AEs leading to study treatment discontinuation are AEs with action taken = "Drug permanently discontinued". Overall summary of AEs leading to discontinuation and treatment-related AEs leading to discontinuation by worst CTC grade will be presented by SOC/PT. By-subject AEs leading to discontinuation listing will be provided.

#### Summary:

• Summary of AEs leading to discontinuation by worst CTC grade (Grade 1, 2, 3, 4, 3-4, 5) presented by SOC/PT

AE leading to discontinuation of cabiralizumab or discontinuation of nivolumab will be included.

• Summary of treatment-related AEs leading to discontinuation by worst CTC grade (Grade 1, 2, 3, 4, 3-4, 5) presented by SOC/PT

Adverse events summarized are those relate to at least one of the combination therapy and lead to discontinuation of at least one of the combination.

### 7.6.4 Adverse Events

Overall summary of any TEAEs and treatment-related TEAEs by worst CTC grade will be presented by SOC/PT. All recorded AEs occurring in the pre-treatment, on-treatment, and post-treatment period will be listed.

#### Summary:

- Summary of any AEs by worst CTC grade (Grade 1, 2, 3, 4, 3-4, 5) presented by SOC/PT
- Summary of treatment-related AEs by worst CTC grade (Grade 1, 2, 3, 4, 3-4, 5) presented by SOC/PT

#### 7.6.5 Select Adverse Events

The select Adverse Events (select AEs) consist of a list of preferred terms grouped by specific category (e.g. pulmonary events, gastrointestinal events categories, etc.). AEs that may differ from or be more severe than AEs caused by non-immunotherapies and AEs whose early recognition and management may mitigate severe toxicity are included as select AEs. The select AEs and the categories are defined by the Sponsor and the list that is the most current at the time of analysis will be used.

#### 7.6.5.1 Incidence of select AEs

Overall summary of any select AEs, treatment-related select AEs, serious select AEs, treatmentrelated serious select AEs, select AEs leading to discontinuation, treatment-related select AEs leading to discontinuation, by worst CTC grade will be presented by category or subcategory/PT. By-subject select AE listing will also be provided.

The following analyses will be conducted:

- Summary of any select AEs by worst CTC grade (grade 1, 2, 3, 4, 3-4, 5) presented by category or subcategory/PT
- Summary of treatment-related select AEs by worst CTC grade (grade 1, 2, 3, 4, 3-4, 5) presented by category or subcategory/PT
- Summary of any serious select AEs by worst CTC grade (Grade 1, 2, 3, 4, 3-4, 5) presented by category or subcategory/PT
- Summary of treatment-related serious select AEs by worst CTC grade (Grade 1, 2, 3, 4, 3-4, 5) presented by category or subcategory/PT
- Summary of any select AEs leading to discontinuation by worst CTC grade (grade 1, 2, 3, 4, 3-4, 5) presented by category or subcategory/PT
- Summary of treatment-related select AEs leading to discontinuation by worst CTC grade (grade 1, 2, 3, 4, 3-4, 5) presented by category or subcategory/PT

### 7.6.6 Other Events of Special Interest

Other events of special interest (AEOSI) consist of a list of preferred terms grouped by specific category (e.g. Myositis Event, Myocarditis Event, Demyelination Event, Guillain-Barre Syndrome, Pancreatitis Event, Uveitis Event, Encephalitis Event, etc.). The list of MedDRA

preferred terms used to identify AEOSI is revisited quarterly and updated accordingly. The preferred terms used for the selection at the time of the database lock by categories will be provided.

Other AEs of special interest will be summarized by treatment group for each category.

- Summary of other AEs of special interest by worst CTC grade (Grade 1, 2, 3, 4, 3-4, 5) presented by Category/PT
- Summary of treatment-related other AEs of special interest by worst CTC grade (grade 1, 2, 3, 4, 3-4, 5) presented by Category/PT
- Summary of serious other AEs of special interest by worst CTC grade (grade 1, 2, 3, 4, 3-4, 5) presented by Category/PT

By-subject listing of other AEs of special interest will be provided.

### 7.6.7 Clinical Laboratory Evaluations

Clinical laboratory data will be analyzed using both US conventional units and international system of units if needed. The on-treatment period starts at first dose and ends at 100 days after last study therapy.

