## **3.1.3 End-of-Treatment Follow-up Period**

All patients should return to the clinic 28 ( $\pm 7$ ) days and 100 ( $\pm 7$ ) days from their last dose of study drug to complete the End-of-Treatment Follow-up Period, irrespective of whether a patient is discontinued from the study drug at a planned visit or mid-cycle. AEs will be assessed until resolution, return to baseline, or are stabilized per treating Investigator's assessment. Adverse

event reporting will continue until 100 ( $\pm 7$ ) days after the last dose of study drug or until initiation of subsequent anti-cancer therapy.

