### 5.2.3.8 End-of-Treatment Follow-up Period

Patients will return to the study center twice, approximately 28 ( $\pm 7$ ) days and 100 ( $\pm 7$ ) days after their last infusion of cabiralizumab and nivolumab to complete the End-of-Treatment Follow-up Period.

The following assessments will be performed:

- Physical examination including weight
- Vital signs (blood pressure, pulse, respiratory rate, pulse oximetry and temperature in resting position after 5 minutes rest)
- ECOG performance status evaluation
- Clinical safety labs (as described in [Appendix B](#))
- 12-lead ECG (28 [ $\pm 7$ ] days post last infusion of cabiralizumab and nivolumab visit only)
- Collect sample if the patient is being followed for a tumor marker (e.g. CA-125, or others)
  - CA-125 is require for cohort 1b5
- Radiological imaging: CT or MRI scan does not need to be repeated if performed within 8 weeks prior to the End-of-Treatment Visits or if tumor progression was previously determined.
- Serum pregnancy test ( $\beta$ -hCG) for women of childbearing potential
- Optional tumor biopsy for patients who progressed (28 [ $\pm 7$ ] days post last infusion of cabiralizumab and nivolumab visit only) (analyses described in [Appendix D](#))
- Blood collection
  - Serum (analyses described in [Appendix D](#))
  - Whole blood (CD14+/CD16+ monocyte analysis and gene expression analysis)
- AE reporting, until 100 ( $\pm 7$ ) days after the last dose of study drug or until initiation of subsequent anti-cancer therapy. Patients with ongoing SAEs will be followed until resolution or stabilization.
- Review of concomitant medications

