### 6.1 Collection of Adverse Events

Any new symptoms, injury or worsening of symptoms that occur following signing of the informed consent form (ICF) but prior to first infusion (Cycle 1 Day 1) will be considered pretreatment events and reported on the Medical History page of the electronic case report form (eCRF), unless they directly correlate to a study-related procedure. Adverse event reporting will continue until 100 ( $\pm 7$ ) days after the last dose of study drug or until initiation of subsequent anti-cancer therapy.

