### Summary:

The number (%) of subjects with the following will be summarized using the worst CTC grade ontreatment per subject.

- Post-baseline grade (summary of worst toxicity grade)
- Grade change from baseline
- Descriptive statistics of laboratory test result and their changes from baseline at scheduled nominal visit.

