## 7.6.7.2 Abnormal Thyroid Test

## Summary:

The number (%) of subjects with abnormal thyroid test will be summarized as follows:

- Elevated TSH value > ULN and one of the below subcategorie is met:
  - with baseline TSH value  $\leq$  ULN
  - with at least one FT3/FT4 test value < LLN within 2-week window after the abnormal TSH test

  - with all FT3/FT4 test values  $\geq$  LLN within 2-week window after the abnormal TSH test
  - with F3/F4 missing within 2-week window after the abnormal TSH test
- Low TSH < LLN and one of the below subcategorie is met:
  - with baseline TSH value  $\geq$  LLN
  - with at least one FT3/FT4 test value > ULN within 2-week window after the abnormal TSH test
  - with all FT3/FT4 test values  $\leq$  ULN within 2-week window after the abnormal TSH test
  - with F3/F4 missing within 2-week window after the abnormal TSH test

The analyses will include lab values up to 100 days after last dose of study drug.

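### The on-treatment window for laboratory tests, vital signs and ECOG runs to 100 days after last dose with no stop at subsequent anticancer therapy, so these summaries can include values taken on the next regimen

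*SAP*

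**What the plan says.** **SAP windows.** Section 7.6.7 defines the laboratory period: "The on-treatment period starts at first dose and ends at 100 days after last study therapy". Sections 7.6.9 (vital signs), 7.6.10 (ECG) and 7.6.12 (ECOG) use the same period. For thyroid tests, 7.6.7.2 says: "The analyses will include lab values up to 100 days after last dose of study drug". The TEAE definition in 7.6 is "adverse event starts or severity becomes worse after the first dose and within 100 days of last study therapy". None of these mentions new anticancer therapy.

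**SAP lab statistics.** Under 7.6.7, post-baseline grade and grade change "will be summarized using the worst CTC grade ontreatment per subject". The hepatic categories (7.6.7.1) and the CK and LDH thresholds (7.6.7.3) also count on-treatment evaluations. No lab table is restricted by attribution to study drug.

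**Protocol AE reporting.** Section 6.1 runs AE reporting to 100 (±7) "days after the last dose of study drug or until initiation of subsequent anti-cancer therapy". Section 6.2.1 applies the same stop to SAEs.

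**Protocol visits.** Section 5.2.3.8 begins "Patients will return to the study center twice, approximately 28" (±7) days, with the second visit at 100 (±7) days. It lists safety labs, vital signs and ECOG for both visits, and a 12-lead ECG for the 28-day visit only. Sections 5.2.1.9 and 5.2.2.11 set the same pattern for Phase 1a. No section exempts patients who have started another treatment.

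**The concern.** The incidence of clinical laboratory abnormalities is a primary safety endpoint in both Phase 1a and Phase 1b (SAP 4.1). AST/ALT, CK and LDH matter particularly for this drug, because the DLT definition in protocol 3.1.2.1.1 makes specific allowances for them.

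A worst-grade statistic is sensitive to one value. If a patient starts another regimen and a draw inside the 100 days shows Grade 3 or 4, that value sets the patient's grade. AE tables have a treatment-related version that can set such events apart; lab tables do not. The AE and lab tables in one report would also describe different periods of risk, and any distortion would vary between cohorts with how quickly patients move to other treatment.

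The SAP already accepts the principle elsewhere. Best overall response uses assessments only up to new anticancer therapy (7.5), and PFS is censored at the last evaluable assessment before it (Table 3).

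**Working it through.** The plan attaches no numerical claim to this rule, so there is no figure of its own to reproduce. The check compares the texts and then sizes the effect under stated assumptions.

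**Step 1. What is collected after a switch, and what the SAP counts**

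| Data | Protocol stop at new therapy? | Scheduled after last dose | SAP window |
|---|---|---|---|
| Hematology and chemistry (including AST, ALT, bilirubin, CK, LDH) | No | Days 28 and 100 (±7) | 100 days, no stop |
| Thyroid panel | No | None; screening and as indicated (Appendices A and B) | 100 days, no stop |
| Vital signs, ECOG | No | Days 28 and 100 (±7) | 100 days, no stop |
| ECG | No | Day 28 (±7) only | 100 days, no stop |
| AEs, SAEs | Yes | Continuous until the stop | 100 days, no stop in the definition |

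For the first three rows, neither document keeps post-switch values out of the summaries. For AEs, the collection rule does most of that work even though the SAP definition is silent.

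**Step 2. How much of the window can fall on the next regimen**

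For a patient who starts new therapy on day s after last dose, days on the next regimen = 100 − s. The values of s are assumed.

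- s = 21: 79 days
- s = 28: 72 days
- s = 42: 58 days
- s = 56: 44 days

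**Step 3. How many scheduled draws that covers**

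A switch before the 28-day visit can contribute two scheduled draws. A switch between the two visits can contribute one, and only if the later visit falls by day 100. That visit may take place on any of days 93 to 107 (15 days), and the last 7 of these, days 101 to 107, lie outside the SAP window. Other post-switch values would have to come from unscheduled tests.

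**Step 4. Illustrative effect on a Grade 3-4 lab rate**

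Let b be the true rate, f the fraction switching before day 100, and q the chance that a switcher has a Grade 3-4 value captured inside the window because of the next regimen, independent of the study-drug effect. All three are assumptions. The cohort size of 30 is the planned Phase 1b size.

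Reported rate = b + (1 − b) × f × q; extra patients = 30 × (1 − b) × f × q. With b = 20%:

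| f | q | Reported rate | Extra patients per 30 |
|---|---|---|---|
| 10% | 10% | 0.20 + 0.80 × 0.01 = 20.8% | 0.24 |
| 30% | 20% | 0.20 + 0.80 × 0.06 = 24.8% | 1.44 |
| 50% | 30% | 0.20 + 0.80 × 0.15 = 32.0% | 3.6 |

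Step 3 bears on q: what matters is a value captured in this study's database, not any toxicity that occurs. With so few scheduled draws, the lower rows of q are the more credible.

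**The case against.** **A long, uncut window is the conservative choice.** Protocol 6.5 equates five half-lives with 90 days, delayed immune toxicity is expected, and protocol 5.3.1 follows study-drug laboratory toxicities until they resolve or stabilize. Cutting at a switch could remove a late hepatic or CK peak that the study drugs caused. This stands, and it is the reason to keep the 100-day summary alongside the truncated one.

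**The consequences are bounded.** All analyses are descriptive (protocol 7). DLTs are judged over the first 28 days, or 42 if extended, so the tail of the window does not drive escalation. SAP 7.6.7 also gives lab statistics by nominal visit, which separates follow-up from dosing-period values. This stands too, but by-visit statistics do not correct the worst-grade tables.

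**Stronger readings that the documents do not support.**

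- *TEAE tables absorb the next regimen's toxicity.* A reader might infer this from the SAP definition alone. The protocol stops new AE and SAE reporting at the switch. What remains is worsening of an event already under follow-up, since "AEs will be assessed until resolution, return to baseline, or are stabilized per treating Investigator's assessment" (protocol 3.1.3), or events recorded outside the rule.
- *ECG summaries are equally exposed.* With one scheduled post-treatment ECG, exposure needs a switch before the 28-day visit or an unscheduled ECG.
- *Post-switch labs are certain to be present.* Protocol 3.1.3 requires the visits "irrespective of whether a patient is discontinued from the study drug at a planned visit or mid-cycle". That clause concerns when treatment stopped, not whether another has begun. The schedule covers all patients without exemption, so such values can be counted; how many will be is not stated.

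**Conclusion.** The concern holds for laboratory tests, vital signs and ECOG. Their summaries can include values obtained on subsequent therapy, and the lab and AE tables do not cover the same risk period. For scheduled hematology and chemistry the route is direct. For thyroid tests it depends on tests done as indicated. For TEAEs and ECGs it is narrow.

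The size cannot be determined from the documents. The range of 20.8% to 32.0% for a true 20% rests entirely on assumed switching (10% to 50%) and capture (10% to 30%). At the more plausible low end it amounts to a fraction of a patient in a cohort of 30. The change is still worth making: the endpoint is primary, the lab tables have no attribution filter, and the correction is cheap.

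**What to change.** 1. In SAP 7.6.7, 7.6.7.2, 7.6.9 and 7.6.12, and for consistency 7.6.10, end the on-treatment period for the main summaries at the earlier of 100 days after last dose and the day before first subsequent anticancer therapy.
2. Keep the full 100-day window as a sensitivity summary, so that late study-drug toxicity in patients who switch remains visible in a table.
3. Write the protocol's stop at subsequent anticancer therapy into the TEAE definition in SAP 7.6. TEAE counts should change little.
4. Leave the hepatic resolution rule in 7.6.7.1 as it is; it deliberately uses all records regardless of the window.

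The date needed is already in the SAP: the survival listing under 7.5.2 includes the date of first subsequent anticancer therapy. The cost is SAP wording, one derived end date and one extra set of tables. The trade-off is slightly shorter lab follow-up in the main summary for patients who switch.

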**Appendix B: Schedule of Assessments – Phase 1b Cabiralizumab + Nivolumab**

Procedure a	Screening	Cycle 1				Cycle 2	Cycle x s	Cycle 8	End-of-Treatment Follow-up Period	Long-Term Follow-up Period t
	Day -28 to Day 0	Day 1 b	Day 2	Day 4	Day 8	Day 1 b	Day 1 b	Days 2, 4, 8	28 (±7) days and 100 (±7) days post-last dose	
	Week 0	Week 1			Week 2	Week 3	Week ≥5			
Informed Consent	x									
Review/Confirm Eligibility Criteria	x	x								
Medical History / Demographics	x	x								
Physical Examination c	x	x			x	x	x		x	
Height and Weight d	x	x				x	x		x	
Vital Signs e	x	x			x	x	x		x	
ECOG Performance Status f	x	x				x	x		x	
Screening Labs g	x									
Clinical Safety Labs h	x	x			x	x	x		x	
12-Lead ECG i	x								x	
CT or MRI Tumor Assessment j,k	x						x		x	x
Serum Pregnancy Test l	x	x					x		x	
Tumor Biopsy m	x						x		x	
PK Sampling n,o		x	x	x	x	x	x	x	x	
PD Sampling n		x		x	x	x	x	x	x	
ADA Sampling n		x				x	x		x	
ANA Sampling p		x				x	x		x	
Study Drugs q,t		x				x	x			
Adverse Events	x-----x									
	[REDACTED]									
Long-Term Follow-up Contacts t										x

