### 7.6.12 ECOG

ECOG performance status will be summarized categorically (ECOG grade: 1, 2, 3, and 4) for each scheduled study visit. Shift tables showing baseline ECOG grade and maximum grade on treatment will be provided. The on-treatment period starts at first dose and ends at 100 days after last study therapy.

A by-subject listing of ECOG will also be provided. Classification of ECOG performance status is provided below.

Performance Status Criteria		
Fully active, able to earry on all pre-disease activities without restriction.		
Restricted in physically strenuous activity but ambulatory and able to carry out work of a light sedentary nature (light housework, office work).		
Ambulatory and capable of all self-care but unable to carry out any work activities. Up and about more than 50% of waking hours.		
Capable of only limited self-care, confined to bed or chair more than 50% of waking hours.		
Completely disabled. Cannot carry on any self-care. Totally confined to bed or chair.		

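### The SAP closes its safety windows at exactly 100 days after last dose, while the last safety visit and AE reporting run to 100 ±7 days, so results from days 101–107 are left out of the incidence and worst-value tables

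*SAP*

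**What the plan says.** **Protocol.** Appendix B sets the End-of-Treatment visits at "28 (±7) days and 100 (±7) days post-last dose"; Appendix A and sections 3.1.3, 5.2.1.9, 5.2.2.11 and 5.2.3.8 agree. Both visits include safety labs, vital signs, weight and ECOG. Sections 3.4, 6.1 and 6.2.1 run AE and SAE reporting to 100 (±7) days after last dose, or to the start of new anti-cancer therapy. SAP 6.1 repeats the ±7-day tolerance for the visits.

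**SAP windows.**
- Laboratory data (7.6.7): "The on-treatment period starts at first dose and ends at 100 days after last study therapy". Vital signs (7.6.9), ECG (7.6.10) and ECOG (7.6.12) use the same limit.
- Thyroid tests (7.6.7.2): "The analyses will include lab values up to 100 days after last dose of study drug".
- TEAEs (7.6): "adverse event starts or severity becomes worse after the first dose and within 100 days of last study therapy".

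**SAP tables that use the window.** Laboratory grades are "summarized using the worst CTC grade ontreatment per subject". The hepatic (7.6.7.1) and CK/LDH (7.6.7.3) threshold tables count on-treatment evaluations. For ECOG, "Shift tables showing baseline ECOG grade and maximum grade on treatment will be provided". Vital signs are summarised by maximum, minimum and last value as well as by visit.

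The SAP text provided contains no visit-window rule that adds the 7 days back.

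**The concern.** The visit tolerance and the analysis cut-off do not match. A patient seen on day 100 contributes that visit's labs, vital signs and ECOG to the worst-value tables. A patient seen on day 101, equally within protocol, does not. Whether a late laboratory abnormality is counted then depends on which permitted day the patient attended.

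The affected tables report primary endpoints: the incidence of AEs and laboratory abnormalities in both phases, and Grade 3 and 4 events in Phase 1b. Removing observations from a worst-grade or ever-exceeded-threshold count can lower it or leave it unchanged, but never raise it. This sits oddly with the SAP's conservative choices elsewhere: missing causality is treated as related, and an AE whose start date is too incomplete to rule it out is treated as a TEAE.

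**Working it through.** The plan gives no figure to reproduce. The check is date arithmetic, in days after last dose.

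**1. Permitted days for the last visit** (protocol, 100 ±7)
- Earliest: 100 − 7 = 93. Latest: 100 + 7 = 107.
- Number of permitted days: 107 − 93 + 1 = 15.

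**2. Permitted days outside the SAP window** (cut-off at day 100)
- Days 101 to 107: 107 − 100 = 7 days.
- Share of permitted days: 7/15 = 46.7%.

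**3. Share of attended visits affected.** The documents do not say when patients attend, so this is an assumption shown as a range.

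| Assumed share of 100-day visits held after day 100 | Visits left out per 100 attended |
|---|---|
| 20% | 20 |
| One third | 33 |
| Uniform over the window (7/15) | 47 |
| 60% | 60 |

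The base is attended 100-day visits, not enrolled patients. Those who die or do not return contribute no visit.

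**4. AEs.** Reporting can run to day 107, and the TEAE window ends at day 100. The uncounted span is 7 of the 107 post-dose days: 7/107 = 6.5%. TEAE status follows the date of onset or worsening, so an AE that began on day 98 and was recorded on day 105 still counts.

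**5. Effect by table**

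| Table | Result from a day 101–107 visit |
|---|---|
| Worst laboratory grade, grade change, hepatic thresholds, CK/LDH thresholds | Left out |
| Vital sign maximum and minimum | Left out |
| ECOG shift to maximum grade | Left out |
| TEAE summaries | Left out only if onset or worsening is on days 101–107 |
| By-visit labs, vital signs, ECOG | Unclear; may be included by nominal visit |
| Thyroid | Little affected: tested at screening and as indicated |
| ECG | Little affected: scheduled end-of-treatment ECG is at the 28-day visit only |
| Hepatic resolution dates, immunogenicity, all deaths, AE listings | Not limited by the cut-off |

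**6. After the change.** With the window extended to day 107 for the nominal 100-day visit, 0 of 15 permitted days fall outside.

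**The case against.** The strongest reply is that a fixed 100-day risk period, applied alike to TEAEs, labs, vital signs, ECG, ECOG and the 100-day death table, is a recognised convention, and that ±7 days is only a scheduling tolerance. This is fair as a design choice. But the SAP does not say that it means to discard compliant final visits. Where it wants data beyond the window (hepatic resolution, immunogenicity), it says so.

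Several stronger readings are tempting and are not supported:

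- **That late toxicity disappears from the report.** It does not. Laboratory by-visit output is described as "Descriptive statistics of laboratory test result and their changes from baseline at scheduled nominal visit", and vital signs and ECOG are also summarised by scheduled assessment or visit, so a day-104 visit could be tabulated there. Listings keep all recorded AEs, and the overall death summary has no cut-off.
- **That the protocol identifies a hazard specific to days 101–107.** The delayed-DLT rule concerns weeks 4 to 6, and section 6.5 puts five half-lives at 90 days. Both lie inside 100 days.
- **That about half of final visits are lost.** This needs uniform attendance, for which there are no data.
- **That the cut-off creates a long gap without scheduled labs.** Most of the gap comes from the visit schedule. The 28-day visit can fall as early as day 21. From there to a fully counted visit on day 93 is already 72 days, against 79 to day 100 and 86 to day 107. Section 5.3.1 also has laboratory toxicities followed locally until they resolve or stabilise.

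The reply does not remove the mismatch in the worst-value, shift, threshold and TEAE tables.

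**Conclusion.** The inconsistency is real but minor. Applied as written, the SAP leaves compliant visits on days 101–107 out of the worst-grade, grade-shift, maximum/minimum and hepatic/CK/LDH tables, and does not count AEs that start or worsen on those days as TEAEs. The direction is certain: incidence counts can only fall. The size is not known. It is 7 of 15 permitted visit days, and 20% to 60% of attended 100-day visits over the assumed range. How many counts would change also depends on how often the final visit shows a patient's worst value, which the documents do not give.

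The conclusion assumes that the programming follows the SAP text, with no visit-window rule held elsewhere. Severity is low because every analysis is descriptive, DLT assessment uses 28 or 42 days, and neither the recommended dose nor ORR rests on this window.

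**What to change.** 1. In SAP 7.6.7, 7.6.9 and 7.6.12, state that the on-treatment period includes the nominal 100-day End-of-Treatment visit when it falls within its ±7-day window, that is, up to day 107. Make the same edit in 7.6.7.2 and 7.6.10 for consistency.
2. In SAP 7.6, align the TEAE window with the AE reporting period: 100 + 7 days after last dose, or the start of subsequent anti-cancer therapy.
3. State whether by-visit summaries are assigned by nominal visit or limited by the on-treatment period.
4. Either footnote that the death table keeps its strict 100-day limit or align it too. Otherwise a fatal AE starting and ending on day 104 would be a TEAE yet absent from the 100-day death table.

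The cost is a small change to a programmed cut-off. It uses data already collected and alters no visit, dose or clinical rule. The window would differ by up to 7 days from a strict 100-day convention; a strict 100-day table can be kept as a supplement where comparability matters. The current TEAE definition has no stop at new anti-cancer therapy, so adding one could exclude any event recorded after that start. The SAP should say so.
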